## **7.2 Prior and Concomitant Therapies**

Administration of medications, therapies, or vaccines will be recorded in the concomitant medication eCRF. Prior medications include recent ( $\leq 90$  days) and current medications and non-COVID-19 vaccinations. Concomitant medications will include all medications (including vaccines) taken by the participant from the time of signing the ICF through EOS (or through the early termination visit if prior to that time). Prescription and over-the-counter (OTC) drugs will be included. Do not record herbals, vitamins, and supplements.

Receipt of all COVID-19 vaccines prior to screening should be recorded in the Vaccine History eCRF. Site staff will record the date(s) and brand of the SARS-CoV-2 vaccine received.

### **7.2.1 Prohibited Therapies**

The following therapies are prohibited within the specified timeframes of study conduct:

- Seasonal influenza vaccine may not be administered  $< 4$  days before or  $< 7$  days after the study vaccine.
- No other vaccine except rabies vaccine (if medically indicated)  $\leq 90$  days before randomization until EOS.
- No investigational product (drug/biologic/device) from time of randomization until after the last study visit.
- No immunoglobulins, monoclonal antibodies, blood products, or any therapy that causes clinically significant immunosuppression within 90 days of study vaccination until the EOS visit. Similarly, rabies immune globulin should be administered if medically indicated.

## 8 SAFETY ASSESSMENTS

The timing and frequency of all safety assessments are listed in the SOE ([Table 1](#)). Recording of unsolicited AEs will be conducted by electronic data capture (EDC). AESIs, including PIMMCs, myocarditis or pericarditis and AESIs specific to complications of potential disease enhancement for COVID-19 or those of specific interest potentially related to COVID-19 vaccines will also be monitored and are to be reported according to timelines specified for SAEs (see [APPENDIX 2](#) for details).

A Central Cardiac Adjudication Committee has been established to adjudicate suspected myocarditis and/or pericarditis cases in the clinical development plan of NVX-CoV2373. Outcomes of the adjudications will be communicated to the Sponsor's SMC.

### 8.1 Definitions

- **Adverse event** – An AE is any untoward medical occurrence associated with the use of an intervention in humans, whether or not it is considered intervention-related. Any abnormal laboratory test results or other safety assessments (eg, physical exam, vital signs measurements) that are clinically significant in the medical and scientific judgment of the Investigator will be considered AEs. An exacerbation of a chronic or intermittent pre-existing condition including either an increase in frequency and/or intensity will be considered an AE.
- **Serious adverse event (SAE)** – An event is considered “serious” if, in the view of either the Investigator or Sponsor, it results in any of the following outcomes:
  - Death
  - A life-threatening AE: An event is considered “life-threatening” if, in the view of either the Investigator or Sponsor, its occurrence places the participant at immediate risk of death. It does not include an AE or suspected adverse reaction (AR) that, had it occurred in a more severe form, might have caused death.
  - Inpatient hospitalization or prolongation of existing hospitalization. In general, hospitalization signifies that the participant has been detained, usually involving an overnight stay, at the hospital or emergency ward for observation and/or treatment that would not have been appropriate in the physician's office or outpatient setting. Hospitalization for an elective treatment of a pre-existing condition that did not worsen from baseline is not considered an SAE.
  - A persistent or significant incapacity or substantial disruption of the ability to conduct normal life functions.
  - A congenital anomaly/birth defect.
  - Important medical events that may not result in death, be life-threatening, or require hospitalization may be considered serious when, based upon appropriate medical judgment, they may jeopardize the participant and may require medical or surgical intervention to prevent one of the outcomes listed in this definition. Examples of such medical events include allergic bronchospasm requiring intensive treatment in an emergency room or at home, blood dyscrasias or convulsions that do not result in inpatient hospitalization, or the development of drug dependency or drug abuse.

- **Causality or relatedness** – For each AE/SAE, the Investigator must document in the medical notes that he/she has reviewed the AE/SAE and has provided an assessment of causality as follows.
  - Not Related: There is no reasonable possibility of relationship to study vaccine. The AE does not follow a reasonable temporal sequence from administration of study vaccine or can be reasonably explained by the participant's clinical state or other factors (eg, concurrent diseases, and concomitant medications).
  - Related: There is a reasonable possibility of relationship to study vaccine. The AE follows a reasonable temporal sequence from administration of study vaccine and cannot be reasonably explained by the participant's clinical state or other factors (eg, concurrent diseases or concomitant medications), represents a known reaction to study vaccine or other vaccines in its class, is consistent with the known pharmacological properties of the study vaccine, and/or resolves with discontinuation of the study vaccine (and/or recurs with re-challenge, if applicable).
- **Adverse reaction** – An AR is any AE caused by the investigational product.
- **Suspected adverse reaction (SAR)** – An SAR is any AE for which there is a reasonable possibility that the investigational product caused the AE. For the purposes of Investigational New Drug (IND) safety reporting, "reasonable possibility" means there is evidence to suggest a causal relationship between the drug and the AE. SAR implies a lesser degree of certainty about causality than AR.
- **Unexpected** – An event is considered unexpected if it is not listed in the IB, is not listed at the specificity or severity that has been observed, or, if an IB is not required or available, is not consistent with the risk information described in the General Investigational Plan or elsewhere in the IND.
- **Severity or intensity** – The severity (or intensity) of an AE/SAE refers to the extent to which it affects the participant's daily activities and will be classified as mild, moderate, or severe using the following criteria:
  - Mild: These events require minimal or no treatment and do not interfere with the participant's daily activities.
  - Moderate: These events result in a low level of inconvenience or require minor therapeutic measures. Moderate events may cause some interference with normal functioning.
  - Severe: These events interrupt a participant's usual daily activity and may require systemic drug therapy or other treatment. Severe events are usually incapacitating.
  - Life-threatening: These events require an ER visit or hospitalization.

If the severity of an AE/SAE changes, the most intense severity should be reported. An AE/SAE characterized as intermittent does not require documentation of the onset and duration of each episode.

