#### 8.2.3.3 Medically Attended Adverse Events

MAAEs are defined as AEs with medically attended visits, including hospital, emergency room, urgent care clinic, or other visits to or from medical personnel for any reason. Routine study visits will not be considered. MAAEs will be reported from the time of study vaccination until Day 29.

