7.2 Analyses of Secondary Endpoint of Safety

As the secondary objective, safety data include MAAEs and AESIs (including myocarditis and/or pericarditis) through Day 29 (ie, 28 days after vaccine dose) and SAEs throughout the study. All safety analyses will be descriptive and conducted using the Safety Analysis Set. Missing data will not be imputed.

MAAEs are defined as AEs with medically attended visits, including hospital, emergency room, urgent care clinic, or other visits to or from medical personnel for any reason. AESIs include PIMMCs, myocarditis or pericarditis (Listings in Appendix 3), AEs specific to COVID-19, or other potential AEs that may be determined at any time by regulatory authorities as additional information concerning COVID-19 is obtained (Listings in Appendix 2). SAE is defined as an event considered “serious” if, in the view of either the Investigator or Sponsor, it results in any of the outcomes listed in Section 8.1 Protocol.

Unsolicited MAAEs and AESIs through Day 29, and SAEs throughout the study will be summarized overall and by the study vaccine group and by SOC/PT using the latest version of MedDRA, as well as by severity (Mild, Moderate, Severe, or Potentially Life Threatening) and relationship (not related, related) to the study vaccine to present the number and percentage with its corresponding exact 95% CIs using Clopper-Pearson method. For multiple occurrences of an AE in the same participant, a participant will be counted only once within an SOC or a PT, using the most severe occurrence and closest reported relationship for the summarization by severity or relationship to the study vaccine, respectively.

The duration of unsolicited AEs including MAAEs and AESIs through Day 29 will be summarized. A by-participant listing of MAAEs and AESIs through Day 29 and SAEs throughout the study will also be provided.

The following summaries of unsolicited AEs will be presented overall and by the study vaccine group as part of the primary analysis of safety:

- Overall summary of all unsolicited TEAEs (Days 1 - 29)
- Summary of all unsolicited TEAEs by MedDRA SOC/PT and severity (Days 1 - 29)
- Summary of all unsolicited TEAEs by MedDRA SOC/PT and relationship to study vaccine (Days 1 - 29)
- Summary of MAAEs by MedDRA SOC/PT and severity (Days 1 - 29)

- Summary of MAAEs by MedDRA SOC/PT and relationship to study vaccine (Days 1 - 29)

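### The protocol's top AE severity grade is set by need for ER or hospital care, which conflicts with its own meaning of life-threatening and with the SAP's label

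*Protocol*

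**What the plan says.** Protocol 8.1 uses the term life-threatening in two places.

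- **Seriousness.** An event is life-threatening if "its occurrence places the participant at immediate risk of death". The text then narrows this: "It does not include an AE or suspected adverse reaction (AR) that, had it occurred in a more severe form, might have caused death". A separate bullet covers "Inpatient hospitalization or prolongation of existing hospitalization". The final bullet, on important medical events that need not be life-threatening, gives as one example "allergic bronchospasm requiring intensive treatment in an emergency room or at home".
- **Severity.** The section describes severity as the effect of the event on daily activities, and says it "will be classified as mild, moderate, or severe using the following criteria". Four grades follow. Mild, moderate and severe are described by interference with activity and by need for treatment. The fourth reads: "Life-threatening: These events require an ER visit or hospitalization".

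Protocol 8.2.3.3 reads: "MAAEs are defined as AEs with medically attended visits, including hospital, emergency room, urgent care clinic", and goes on to other visits to or from medical personnel. Protocol Table 2 makes the severity of MAAEs and AESIs through Day 29 part of a secondary safety endpoint.

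SAP 7.2 summarizes MAAEs, AESIs and SAEs "as well as by severity (Mild, Moderate, Severe, or Potentially Life Threatening" and gives no definition of the last category. Protocol 9.3.3 and SAP 7.2 count a participant once within an SOC or PT, at the most severe occurrence.

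**The concern.** A severity grade should describe how intense an event was. The fourth grade instead describes what care the event called for, and carries a name that the same section reserves elsewhere for immediate risk of death. The two meanings pick out different sets of events, and the SAP adds a label that matches neither.

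The wording bears directly on the events this trial collects. MAAEs include hospital and ER visits by definition, and each participant is counted at the worst grade. A reader of the safety tables would take the top row to mean danger to life, when as written it means a judged need for ER or hospital care. Sites that notice the conflict may also resolve it differently from one another.

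**Working it through.** No figure in the plan is at issue, so the check sets the texts against each other.

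| Question | Protocol 8.1, seriousness | Protocol 8.1, severity | SAP 7.2 |
|---|---|---|---|
| Name of the category | Life-threatening | Life-threatening | Potentially Life Threatening |
| What defines it | Immediate risk of death | Requiring an ER visit or hospitalization | Not defined |
| Place of hospitalization | A separate criterion | Part of the definition | Not stated |
| Number of grades | Not applicable | Three announced, four listed | Four |

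1. **Do the two protocol meanings differ in substance?** Yes. The seriousness text lists hospitalization apart from danger to life, and its bronchospasm example is an event treated in an emergency room that may not be life-threatening. The severity text would put that same event, if it required the ER, in the Life-threatening grade.

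2. **Can one event carry contradictory entries?** Yes. Protocol 8.2 records severity and seriousness for each AE. Section 8.1 describes hospitalization as usually involving an overnight stay. An event that requires an ER visit and is treated and released can therefore be non-serious and still be graded Life-threatening. Under the seriousness text, a life-threatening AE is serious by definition.

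3. **Does another scale override Section 8.1?** None was found. The protocol's change history (Appendix 1, Version 3.0) records that the appendix of FDA grading criteria was removed because those criteria will not be used, and the current list of appendices holds only the change history and the AESI listings.

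4. **Which way does the count move?** Let A be the events with immediate risk of death, and B the events judged to require an ER visit or hospitalization. The severity text puts B in the top grade; the seriousness meaning would put A there. On the assumption that an event with immediate risk of death ordinarily requires ER or hospital care, A lies within B, so the count in B is at least the count in A. Counting each participant at the most severe occurrence preserves this ordering.

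5. **How large is the difference?** It is the number of events in B but not in A. That needs an MAAE rate, the share judged to require ER or hospital care, and the share of those without immediate risk of death. The documents give none of these.

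6. **Which outputs are touched?** SAP 7.2 plans severity tables for all unsolicited TEAEs, MAAEs, AESIs and SAEs. Protocol Table 5 lists an ER visit among the procedures for probable or confirmed myocarditis or pericarditis, so such a case could reach the top grade through its work-up alone. SAP 11.5 also plans a top-level summary of severe AEs and does not say whether the fourth grade is included.

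**The case against.** The strongest reply is that severity and seriousness are different concepts, recorded as separate variables. The judgement about immediate risk of death is therefore kept whatever the grade, and the severity wording does not overwrite the SAE definition. That is right as far as it goes. It limits the damage, but it does not justify one term with two meanings in one section, or a grade that departs from the daily-activities basis the section sets for severity.

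The reply also points to limited consequences, and this stands. All safety analyses are descriptive. The vaccination pause rule uses the Table 4 case definitions, and SAEs and AESIs are reported within 24 hours regardless of grade. By-participant listings let individual events be examined. One scale applies to three randomized, observer-blinded lots.

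Three stronger readings are tempting, and the documents do not support them.

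- A reader might infer that every MAAE seen in an ER, even a minor injury, becomes life-threatening. The severity text says the event must require such care, whereas the MAAE definition turns on visits that took place. Attendance is not the same as need. The word require is undefined, so grading is uncertain, but it does not sweep in all ER attendances.
- A reader might infer that the tables will contradict the SAE forms. Those forms are not in the documents, and an ER visit that meets no seriousness criterion would not be an SAE at all.
- A reader might attach a number of participants by assuming an MAAE rate among the 900 enrolled and a share with ER care. Both inputs would be guesses, so the resulting count should carry no weight.

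**Conclusion.** The point holds as a conflict of definitions that produces a misleading result when the severity scale is followed as written. The protocol announces three grades and lists four. It defines the fourth by need for ER or hospital care, against its own meaning of life-threatening, and the SAP names that grade differently without defining it.

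The direction is established: the top-grade count is equal to or higher than under the immediate-risk meaning, given that events with immediate risk of death ordinarily require ER or hospital care. The size is not established and cannot be derived from the documents.

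The consequence is a distorted absolute severity profile in descriptive tables for a secondary endpoint. With a common scale and blinded assessment, no bias between lots is expected. The primary IgG equivalence analysis does not use these data. The point merits correction because the wording is plainly inconsistent and cheap to repair, not because it threatens the trial's main conclusion.

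**What to change.** Reconcile the seriousness and severity texts in Protocol 8.1 with SAP 7.2 before severity is tabulated. Either of two forms would do:

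- keep the three announced grades and drop the fourth from the protocol and the SAP; or
- keep four grades, announce four, and define the fourth so that it agrees with the seriousness meaning of life-threatening.

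Use one label in the protocol, the SAP and the eCRF completion guidance. If four grades are kept, state in SAP 11.5 whether the summary of severe AEs includes the fourth.

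Hospitalization remains recorded as a seriousness criterion, so that information is not lost. Whether ER attendance has its own field cannot be seen: the AE variables listed in Protocol 8.2 include no place-of-care item. If the sponsor wants ER attendance tabulated, the eCRF should be checked first.

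The cost is a wording change and revised completion guidance. If events have already been graded, those in the top grade would need review against the reconciled definition before database lock.

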## 8.2 Documenting Adverse Events

Reactogenicity reactions will be collected if they meet the criteria for a MAAE, SAE, or AESI.

At every study visit following Screening, participants will be asked a standard question to elicit any medically related changes in their well-being. They will also be asked if they have been hospitalized, had any accidents, used any new medications, or changed concomitant medication regimens (both prescription and OTC medications).

Care will be taken not to introduce bias when detecting MAAEs and SAEs. Open-ended and non-leading verbal questioning of the participant is the preferred method to enquire about AE occurrences. AESIs will be inquired about according to the specific disorders listed in [APPENDIX 2](#).

When an AE/SAE occurs, it is the responsibility of the Investigator to review all available documentation (eg, hospital progress notes, laboratory reports, and diagnostics reports) related to the event. The Investigator will then record all relevant AE/SAE information in the eCRF.

It is not acceptable for the Investigator to send photocopies of the participant's medical records in lieu of completion of the AE/SAE eCRF page. There may be instances when copies of medical records for certain cases are requested. In this case, all participant identifiers, with the exception of the participant number, will be redacted on the copies of the medical records before submission. The Investigator will attempt to establish a diagnosis of the event based on signs, symptoms, and/or other clinical information. Whenever possible, the diagnosis (not the individual signs/symptoms) will be documented as the AE/SAE.

The following variables will be recorded for each AE: verbatim/AE description and date for AE start and stop, severity, seriousness, causality, any other action taken, and the outcome.

#### 8.2.1.1 Assessment of Causality

There may be situations in which an SAE occurs and the Investigator has minimal information to include in the initial report. However, it is very important that the Investigator always makes an assessment of causality for every event before the initial transmission of the SAE data. The Investigator may change their opinion of causality in light of follow-up information and send a SAE follow-up report with the updated causality assessment. The causality assessment is one of the criteria used when determining regulatory reporting requirements.

The investigator should consider the following, before reaching a decision on causality assessment:

- Time relationship between study vaccine injection and event's onset.
- Re-challenge following second vaccination, if applicable.
- Medical history.
- Study treatment.
- Mechanism of action of study vaccine.
- Class effect (adjuvanted protein vaccines).
- Concomitant treatments in use.
- Withdrawal of study treatment.
- Lack of efficacy/worsening of existing condition.
- Possible vaccine enhancement of COVID-19.

### 8.2.2 Time Frame for Collection

AEs reported or observed during the study will be recorded on the AE page of the eCRF.

Medical occurrences that begin prior to administration of the study vaccine will be recorded on the Medical History/Current Medical Conditions section of the eCRF not the AE section.

All AESIs and MAAEs will be collected from the time of study vaccination until EOS.

All SAEs will be collected from signing of informed consent until completion of the EOS.

All vaccine administration errors, MAAEs, SAEs, cases of multisystem inflammatory syndrome, and hospitalized or fatal cases of COVID-19 following vaccination must be reported based on local regulatory reporting guidance for safety events.

At any time after completion of the EOS visit, if an Investigator learns of an SAE that could reasonably be considered related to study vaccine, he/she should promptly notify the Sponsor.

### 8.2.3 Classification of Events

#### 8.2.3.1 Treatment-Emergent Adverse Event

Treatment-emergent adverse events are defined as any AE occurring or worsening on or after the dose of study vaccine.

#### 8.2.3.2 Adverse Events of Special Interest

Participants will be assessed for diagnosis of an AESI at all study visits. AESIs include PIMMCs, myocarditis or pericarditis, AEs specific to COVID-19, or other potential AEs that may be determined at any time by regulatory authorities as additional information concerning COVID-19 is obtained. Listings of AESIs are presented in [Appendix 2](#).

##### 8.2.3.2.1 Myocarditis and/or Pericarditis (CDC Definition)

Participants reporting signs or symptoms of myocarditis or pericarditis (fatigue, acute chest pain, shortness of breath, etc.[see [Table 4](#)]) within 4 weeks after vaccination should be evaluated as soon as possible by a physician who should initiate a diagnostic work up including, but not limited to, laboratory tests and initial cardiac evaluation. If probable or confirmed myocarditis and/or pericarditis is diagnosed after the initial evaluation, all efforts will be made to route the participants to be followed up preferentially by a cardiologist or pediatric cardiologist (as applicable) who should complete the initial evaluation and manage cases following current practice guidelines (eg, AHA or other national/local guidelines); this might include performing functional cardiac evaluation and follow up of the case until resolution (see [Table 5](#)). A Central Cardiac Adjudication Committee has been established to adjudicate probable myocarditis and/or pericarditis cases in the clinical development plan of NVX-CoV2373. Outcomes of the adjudications will be communicated to the SMC (when applicable) and to the Sponsor.

All myocarditis and/or pericarditis signs and symptoms, as well as all clinical evaluations, will be considered part of the study record and should be documented in the relevant eCRF pages. Participants with confirmed myocarditis or pericarditis will be followed-up to document resolution of symptoms and/or abnormal test findings.

